4 STUDY DESIGN

4.1 Overall Design

This is a randomized, single-center, open-label feasibility trial to provide preliminary signals of performance to help make decisions about whether to continue with the development of product enhancements. Four variations of the BD Nexiva PIVC (20G x 1, 20G x 1.75, 22G x 1, or 22G x 1.75) will be placed in the lower cephalic vein of both arms in approximately 40 healthy volunteers; 20 participants with 20G x 1 inch and 20G x 1.75 inch catheters, and second group of 20 participants with 22G x 1 inch and 22G x 1.75 inch catheters. PIVC indwell time will be monitored (removal at 72 hrs or upon inability to flush/aspirate) with blood collected by venipuncture (Day 1 only) and via the devices using 2 and 6mL vacutainers throughout the remainder of indwell time.

After 5 participants have completed their final visit, the in-situ catheter positions will be compared to the expected tip position based on the catheter lengths (1 inch versus 1.75 inch for either gauge). Tip position of the longer catheter is expected to reside more horizontally within the vessel. In the event catheter tip position differences are not distinct between catheter device lengths study conduct may be stopped. Additionally, this analysis will be used to refine study logistics associated with device placement, securement, sonographic measurements, and blood sample acquisition/testing over the 72-hour study duration.

Each participant will complete 6 visits: a Screening Visit (V1), followed by 4 Visits (V2-V5) to be started within 30 days after screening, and a 24-96 hour follow-up post catheter removal (V6).

The duration of the study execution is expected to be 5 months.

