2.8 Endpoints

2.8.1 Primary Endpoint

The primary endpoint is the catheter indwell time, defined as the time from catheter insertion to time of catheter failure. It is measured in hours.

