5.2.1 Statistical Analysis of Primary Endpoint

5.2.1.1 Indwell Time

It is hypothesized that:

- PIVC indwell time will be greater for longer catheters
- PIVC indwell time will be greater for catheters of smaller gauge (larger bore)

In order to test these hypotheses, catheter indwell time will be assessed using survival analysis, including:

- Kaplan-Meier survival curves including Log-Rank test p-value
- Cox Proportional Hazards Model with Hazard Ratios for each device vs. default device condition (BD Nexiva 20G x 1 inch) and associated 95% Confidence Intervals. Effect of the following covariates will be investigated: gender, age, BMI and dominant arm.

Main analysis will be performed stratified by device, depending on the results pooled analyses by gauge or by catheter length might be performed. An example of the Kaplan-Meier curve and associated metrics is provided in Appendix B by Figure B.1.1. An example of the Hazard Ratios extracted from the Cox Proportional Hazards models is provided in Appendix A by Table A.4.2.

For the purpose of this survival analysis, device failure (inability to flush or draw blood, see section 6.6) will be identified as follows:

- Blood Draw: Variables DEBLDCS equal to “N” and DEBLDRS equal to “N” from table INBCINBC
- Flush: Variables DEFLSSU equal to “N” and DEFLSRS equal to “N” from table INFL

Failure can occur during any of the 7 repeats of the blood draw (for either tube volumes) or flush processes, as highlighted in orange on Table 2.7.1, for right or left arm, per randomization schedule. Date-time of failure is then given by the aggregation of variables DEDTN & DEFTM, from tables INBCINBC or INFL, respectively for blood draw or flush.

Additional Indwell Time summary statistics and graphical representation will be provided as represented in Appendix A by Table A.4.1 and in Appendix B by Figure B.2.1, respectively.

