5.2.4 General Considerations

- For categorical data, count and percentage with 95% confidence interval will be calculated.
- For continuous data, average, standard error, 95% confidence interval, median, inter-quartiles, minimum and maximum will be provided.
- p-values less than 0.05 will be considered statistically significant. Multiple comparisons adjustments (Tukey's or Sydak's) will be made when appropriate
- Importance of factors/variables might be evaluated using machine learning tools such as the Boruta algorithm (random forest all-relevant approach)

- Whenever possible, effects of the following covariates will be investigated: gender, age and BMI
- Initially, all factors/variables will be included into the model as well as any two-way/three-way interactions.
- Variables or interactions which are not significant ($p\text{-value} < 0.05$) will be removed from the final model. Models adjusted with significant effects (and significant interactions if any) will be used for analysis whenever possible.
- Use of models will be preferred to non-parametric tests whenever possible.
- Residual plots for each model will be drawn and reviewed to ensure there are no systematic patterns.
- Transformation of response and/or explanatory variables will be investigated whenever modeling assumptions are not satisfied.

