	No	6 (30.0%)	8 (40.0%)	14 (35.0%)
	Total	20	20	40
	Blood Draw Fill Time (sec)			
	Mean	39.48	39.15	39.31
95% Mean CI	37.86, 41.08	37.41, 40.86	38.10, 40.51	
Median	39.40	39.92	39.74	
SD	3.83	4.06	3.90	
Min, Max	32.77, 46.32	32.06, 46.4	32.06, 46.4	
Total Count	20	20	40	
6mL	cfHb (mg/dL)			
	Mean	194.94	200.96	197.95
	95% Mean CI	174.19, 215.28	178.16, 223.07	182.86, 213.25
	Median	212.88	193.48	207.24
	SD	47.91	52.64	49.77
	Min, Max	86.01, 275.98	103.33, 311.35	86.01, 311.35
	Total Count	20	20	40
	Haemolysis - AU480 (Yes/No)			
	Yes	12 (60.0%)	9 (45.0%)	21 (52.5%)
	No	8 (40.0%)	11 (55.0%)	19 (47.5%)
Total	20	20	40	
Haemolysis - Visual (Yes/No)				
Yes	13 (65.0%)	13 (65.0%)	26 (65.0%)	
No	7 (35.0%)	7 (35.0%)	14 (35.0%)	
Total	20	20	40	
Blood Draw Fill Time (sec)				
Mean	99.94	101.73	100.83	
95% Mean CI	97.33, 102.41	98.61, 105.01	98.85, 102.95	
Median	101.04	100.15	100.15	
SD	5.98	7.49	6.75	
Min, Max	86.61, 108.96	91.1, 116.4	86.61, 116.4	
Total Count	20	20	40	

A.4 Indwell Time

Table A.4.1: Numerical Summary of Subjects Indwell Time in hours, per Device Configuration (Gauge and Length) and Overall

Characteristic	BD Nexiva (22G x 1 inch)	BD Nexiva (22G x 1.75 inch)	BD Nexiva (20G x 1 inch)	BD Nexiva (20G x 1.75 inch)	Overall
Indwell Time (Hours)					
Mean	44.76	55.84	59.72	69.82	57.54
95% Mean CI	36.08, 53.42	45.68, 64.78	52.74, 65.55	68.08, 71.24	53.19, 61.60
Median	42.84	66.22	64.09	72.00	66.97
SD	20.38	22.59	14.76	3.83	18.97
Min, Max	9.4, 72	0.07, 72	15.76, 72	58.6, 72	0.07, 72
Total Count	20	20	20	20	80

Table A.4.2: Proportional Hazard Ratios computed from Cox Proportional Hazards model for Indwell time

	HR(95%CI)	P(Wald's test)	P(LR-test)
device: ref.=BD Nexiva (22G x 1 inch)			0.002
BD Nexiva (22G x 1.75 inch)	0.6 (0.28,1.26)	0.175	
BD Nexiva (20G x 1 inch)	0.57 (0.27,1.2)	0.141	
BD Nexiva (20G x 1.75 inch)	0.2 (0.08,0.49)	< 0.001	

A.5 Indwell Failure Mode

Table A.5.1: Failure Modes Count Overall

Failure Mode	Flush	Draw (2mL)	Draw (6mL)
Unsecure Luer Connection	2	0	1
Locked Clamps	2	0	0
Catheter Dislodgement	5	0	0
Catheter Kinking	2	2	0
Vasospasm	0	0	0
Thrombus	24	10	7
Infiltration	2	0	0
Other	9	0	1

A list of the failure modes available in the free form text field describing the “Other” category will be provided.

Table A.5.2: Failure Modes Count Per Device Configuration

Device	Failure Mode	Flush	Draw (2mL)	Draw (6mL)
BD Nexiva (22G x 1 inch)	Luer Connection	0	0	0
	Clamp	1	0	0
	Tube Kinking	0	0	0
	Dislodgement	0	0	0
	Catheter Kinking	1	0	0

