subjID	gauge	bloodDisorderClotting	cancer	heartDisease	highBloodPressure	diabetesType2
S001	22G	No	No	No	No	Yes
S002	20G	No	No	No	No	No
S003	20G	No	No	No	No	No
S004	22G	No	No	No	Yes	No
S005	22G	Yes	No	No	No	Yes
S006	20G	No	No	No	Yes	No
S007	20G	No	No	No	No	No
S008	22G	Yes	No	No	No	Yes
S009	22G	No	No	No	No	Yes
S010	22G	No	No	No	No	No
S011	20G	No	No	No	No	Yes
S012	20G	No	No	No	No	No
S013	20G	No	No	No	Yes	No
S014	22G	No	No	No	No	No
S015	20G	No	No	No	Yes	No
S016	22G	No	No	No	No	No
S017	20G	No	No	No	Yes	No
S018	22G	No	No	No	No	No
S019	22G	No	No	No	No	No
S020	20G	No	No	No	Yes	No
S021	22G	No	No	No	No	No
S022	20G	No	Yes	No	Yes	No
S023	22G	No	No	No	No	No
S024	20G	No	No	No	No	No
S025	20G	No	No	No	Yes	No
S026	20G	No	No	No	No	No
S027	22G	No	No	No	No	Yes
S028	22G	No	Yes	No	No	No
S029	20G	No	No	No	No	No
S030	20G	No	No	No	No	No
S031	22G	No	No	No	No	No
S032	22G	No	No	No	No	No
S033	22G	No	No	No	No	No
S034	20G	No	No	No	No	No
S035	22G	No	No	No	No	Yes
S036	20G	No	No	No	No	No
S037	20G	No	No	No	No	No
S038	20G	No	No	No	No	No
S039	22G	No	No	No	No	No
S040	22G	No	No	No	No	No

Table C.0.4: Dummy Baseline listing (rows 1 to 40).

subjID	gauge	tipMidStream	tipWallContact	bfv	cv_ratio
S001	22G	Yes	No	162.86	35.70
S002	20G	Yes	No	169.78	33.96
S003	20G	Yes	Yes	157.73	39.69
S004	22G	Yes	Yes	151.31	42.67
S005	22G	No	No	165.24	36.42
S006	20G	No	No	164.16	44.91
S007	20G	Yes	No	168.51	35.11
S008	22G	No	No	163.64	30.23
S009	22G	Yes	No	173.14	33.27
S010	22G	Yes	No	164.40	40.57
S011	20G	Yes	No	159.85	41.06
S012	20G	No	No	173.71	37.45
S013	20G	Yes	Yes	160.25	42.14
S014	22G	Yes	No	166.91	31.00
S015	20G	Yes	No	155.56	44.65
S016	22G	Yes	No	159.83	35.38
S017	20G	Yes	No	163.14	42.58
S018	22G	Yes	No	161.69	38.99
S019	22G	No	No	159.15	34.75
S020	20G	Yes	No	151.37	43.20
S021	22G	Yes	No	163.94	34.72
S022	20G	Yes	Yes	169.70	42.95
S023	22G	No	No	164.49	40.26
S024	20G	Yes	No	161.92	32.11
S025	20G	Yes	No	173.03	42.02
S026	20G	No	No	154.34	33.76
S027	22G	Yes	Yes	155.45	41.91
S028	22G	Yes	Yes	155.20	30.45
S029	20G	Yes	No	169.53	33.37
S030	20G	Yes	No	157.41	35.70
S031	22G	Yes	No	150.97	33.86
S032	22G	Yes	No	157.20	33.50
S033	22G	Yes	No	158.89	33.09
S034	20G	Yes	Yes	161.70	38.45
S035	22G	No	No	173.17	39.35
S036	20G	Yes	No	158.18	39.31
S037	20G	No	No	150.46	33.90
S038	20G	Yes	No	158.48	37.64
S039	22G	Yes	No	173.28	40.17
S040	22G	Yes	No	156.54	32.07

Table C.0.5: Dummy Indwell Time listing (rows 1 to 40).

subjID	device	lifeTime	indwellTime_cont	status	eventType	indwellTime_disc

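### Table A.4.1 summarises a time-to-failure endpoint by plain mean, SD and median, which understate time to failure if working catheters leave before 72 h

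*SAP*

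**What the plan says.** SAP 2.8.1 makes the primary endpoint a time-to-event variable, "defined as the time from catheter insertion to time of catheter failure". Protocol 4.1 sets the end of observation: "removal at 72 hrs or upon inability to flush/aspirate".

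SAP 5.2.1.1 analyses the endpoint by Kaplan-Meier curves with a log-rank test and by Cox models. It then says: "Additional Indwell Time summary statistics and graphical representation will be provided as represented in Appendix A by Table A.4.1". The shell in Appendix A.4, titled "Numerical Summary of Subjects Indwell Time in hours, per Device Configuration (Gauge and Length) and Overall", has rows for mean, 95% mean CI, median, SD, minimum and maximum, and a total count of 20 per configuration and 80 overall. It has no row for failures or censored catheters. SAP 5.2.4 applies the same kind of summary to all continuous variables, without an exception for censored times: "For continuous data, average, standard error, 95% confidence interval, median, inter-quartiles, minimum and maximum will be provided".

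Listing C.0.5 carries the columns "lifeTime indwellTime_cont status eventType indwellTime_disc", so a failure flag exists for each catheter. Table A.4.1 makes no visible use of it.

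**The concern.** A plain average of times in place treats each censored time as if the catheter had failed then. If a catheter is still working when it leaves the study, its time to failure is longer than the recorded time, so the average is too low.

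SAP 5.2 gives the estimation of absolute effects a weight similar to that of significance. Table A.4.1 is the only table shown that states indwell time in hours, because Table A.4.2 gives hazard ratios only. The preliminary analysis in SAP 2.6 reports indwell time as described in 5.2.1.1, so these figures could reach decision makers before database lock.

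**Working it through.** **1. What the shell computes.** The dummy means in Table A.4.1 are "44.76 55.84 59.72 69.82 57.54" and the SDs "20.38 22.59 14.76 3.83 18.97" (22G x 1, 22G x 1.75, 20G x 1, 20G x 1.75, overall).
- Overall mean: (44.76 + 55.84 + 59.72 + 69.82)/4 = 57.535, as printed (57.54).
- Overall SD: within-group sum of squares 19 × Σ SD², plus between-group sum of squares 20 × Σ (mean − 57.535)², divided by 79, square root = 18.97, as printed.

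The overall column is therefore ordinary arithmetic on all 80 times. That censored times are among them is an inference from the full counts and from listing C.0.5.

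**2. Censoring in the dummy listing.** Listing C.0.5 shows 40 catheters (20 participants). Status is 1 for 22 and 0 for 18. Of the 18, 9 are at 72 h and 9 are earlier (28.76 to 70.67 h).

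**3. Plain statistics against Kaplan-Meier on that listing** (10 catheters per configuration). The restricted mean is the area under the Kaplan-Meier curve to 72 h. For 20G x 1:
- Plain mean: 603.50/10 = 60.35 h.
- The catheter censored at 37.93 h leaves 9 at risk at the first failure (43.29 h). The curve then steps to 8/9, 7/9, 6/9 and 5/9 at 43.29, 53.34, 57.79 and 61.96 h.
- Restricted mean: 43.29 + (8/9)(10.05) + (7/9)(4.45) + (6/9)(4.17) + (5/9)(10.04) = 64.04 h.

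| Configuration | Failed / censored before 72 h / at 72 h | Plain mean | Restricted mean | Plain median | KM median |
|---|---|---|---|---|---|
| 22G x 1 | 7 / 2 / 1 | 46.06 | 49.29 | 40.39 | 43.54 |
| 22G x 1.75 | 6 / 2 / 2 | 61.81 | 62.82 | 68.71 | 72.00 |
| 20G x 1 | 6 / 3 / 1 | 60.35 | 64.04 | 63.28 | 72.00 |
| 20G x 1.75 | 3 / 2 / 5 | 69.82 | 70.28 | 72.00 | not reached |
| Overall | 22 / 9 / 9 | 59.51 | 61.92 | 67.72 | 72.00 |

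The plain mean is lower in all four configurations, by 3.2, 1.0, 3.7 and 0.5 h. For 20G x 1.75 the plain median prints as 72.00 although the Kaplan-Meier estimate at 72 h is 67% still patent.

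**4. Where the bias in the mean comes from.** With censoring only at 72 h, the mean of min(T, 72) is by definition the restricted mean. A simulated check on 20 catheters gave 43.64 h both ways. The bias in the mean therefore comes only from non-failure exits before 72 h.

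**5. Size under an assumed exit rate.** Assume exponential failure at rate λ = ln 2/median and independent exponential removal at rate μ = −ln(1 − p)/72, where p is the chance of removal by 72 h in the absence of failure. Let S = exp(−72λ).
- Restricted mean = (1 − S)/λ
- Plain mean = [1 − S(1 − p)]/(λ + μ)
- Plain median = ln 2/(λ + μ)

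True median 72 h: λ = 0.009627, S = 0.5, restricted mean = 0.5/0.009627 = 51.9 h.

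| p | λ + μ | Plain mean (h) | Gap in mean (h) | Plain median (h) |
|---|---|---|---|---|
| 5% | 0.010339 | 0.525/0.010339 = 50.8 | 1.2 | 67.0 |
| 10% | 0.011090 | 0.550/0.011090 = 49.6 | 2.3 | 62.5 |
| 20% | 0.012726 | 0.600/0.012726 = 47.1 | 4.8 | 54.5 |

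True median 24 h: restricted mean 0.875/0.028881 = 30.3 h. The plain means are 29.8, 29.2 and 28.1 h, gaps of 0.5, 1.0 and 2.2 h. The plain medians are 23.4, 22.8 and 21.7 h.

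**The case against.** The strongest reply is that nothing inferential rests on this table. SAP 5.2.1.1 calls it additional, and the planned Kaplan-Meier, log-rank and Cox methods handle censoring. That stands. A reader might infer that the trial's main indwell result is biased; the documents do not support this. Figure B.1.1 is also promised with associated metrics that are not visible here, and these may already include Kaplan-Meier medians.

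Early exits may be few. Protocol 8.1 expects withdrawal to be uncommon, Protocol 8.3 replaces those who leave, Protocol 10.3 defines an evaluable set followed to failure or 72 h, and SAP 6.2.1 excludes suspected tampering and repeated non-attendance. These reduce the problem without removing it: SAP section 4 defines no completers-only set for this table, and SAP 5.2.5 rules out imputation.

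The listing is dummy data and is not a forecast of early censoring. Some rows are incoherent: two 1.75-inch catheters (S004 and S015) have lifetimes of 86.02 and 92.07 h, capped at 72.00, yet are flagged as failures. Such rows do not change the 72-h restricted mean, but they do affect the Kaplan-Meier medians of 72.00 above.

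Two stronger readings are tempting.
- **Adverse-event removals are wrongly counted as failures.** SAP 6.6 and Protocol 7.6 define such removal as failure, so counting it at its removal time is correct under that definition. What the documents do show is that the event coding in SAP 5.2.1.1 uses only flush and blood-draw variables, which does not match 6.6. The status of accidental dislodgement is similarly unclear: SAP 5.2.3.1 lists it as a removal reason separate from flush or draw failure, while the mock failure-mode tables count dislodgement under flush.
- **The bias is larger for the better device.** This holds in the model above, where removal hazards are equal. In the dummy listing the best configuration, 20G x 1.75, has the smallest gap in the mean (0.5 h).

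**Conclusion.** The point holds as a defect in the format of a supplementary table. Table A.4.1 ignores the status flag, so its mean and median understate time to failure whenever a working catheter leaves before 72 h without failing, for example on participant withdrawal or on any removal not coded as a failure. It can also show a median of 72.00 that has not been reached.

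The size depends on an early-exit rate that the documents do not give; the sample-size calculation in SAP 2.4 assumes no loss. For 5% to 20% removal, the mean is low by 1.2 to 4.8 h if the true median is 72 h, and by 0.5 to 2.2 h if it is 24 h. The corresponding shortfall in the median is 5.0 to 17.5 h and 0.6 to 2.3 h. These figures rest on exponential failure and non-informative removal. With no early exits the bias in the mean is zero. Severity is minor.

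**What to change.** In Table A.4.1, report for each configuration the Kaplan-Meier median (or 'not reached') and the mean restricted to 72 h, each with a 95% CI. Add the numbers failed, censored at 72 h and censored earlier. If the plain statistics and the boxplot (Figure B.2.1) are kept, label them as observed time in place, capped at 72 h.

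Reconcile the failure definition in SAP 6.6, which includes adverse-event removal, with the flush and blood-draw coding in SAP 5.2.1.1, so that these removals are classified in the same way throughout.

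The cost is a revised table shell and a few sentences in the SAP. No further data need be collected, and the planned tests do not change as a result of the table revision.

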5.1.7 Flush pressure profile and duration of flush

The flush pressure profile (i.e. duration and peak pressure) will be derived from the pressure trace from a 3 to 10 mL saline flush performed upon first accessing the device at each time point indicated in Table 2.7.1. Pressure (P) will be recorded prior to commencement of the flush and this will be defined as “baseline” pressure. Commencement of the flush will induce a spike in positive pressure, and this will be defined as “time point zero” (t_0). The time point at which the spike in positive pressure returns to baseline will indicate completion of the flush and will be defined as the “completion time point” (t_c). Subsequently, the duration of the flush will be derived by subtracting time point zero from the completion time point, as described in Equation 2.

$$\text{flush duration} = t_c - t_0 \quad (2)$$

Alternatively, the duration of the flush could be reduced to the time between the max pressure and the completion time point, as described in Equation 3.

$$\text{alternative flush duration} = t_{max} - t_0 \quad (3)$$

The pressure reading with the maximal value between the two time points will be recorded as the peak pressure, defined as in Equation 4.

$$\text{flush peak pressure} = \max_{t_0 < t < t_c} P(t) \quad (4)$$

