5.2.1.3 Additional Description of Failure Remediation

Failure remediation counts, which steps are described in the PIVC rescue decision trees for flush and aspiration procedures represented in Appendix D by Figures D.1.1 and D.1.2, will be summarized for each step overall and per device per day, as represented in Appendix A by Tables A.7.1 and A.7.2, respectively.

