5.2.3.2 Flush pressure profile

Manual flush variability will be evaluated using duration of flush and characteristics of Flush pressure profile obtained on in-line pressure measurements. They will be comprised of:

- Peak pressure
- Flush duration (sec.)

For each of these characteristics, summary statistics by indwell time considered as a discrete variable (0, 6, 24, 30, 48, 54, 72 hours) and longitudinal line and bar plots will be generated on average for continuous and by proportion for categorical responses, respectively.

Lineplots will be similar to the example provided for cfHb in Figure B.3.2 and bar plots will be similar to the example provided for Haemolysis occurrence in Figure B.4.1, both represented in Appendix B.

Relationship between the occurrence of these events will be investigated using the Boruta algorithm with a survival random forest model (an example output from the algorithm is provided in the Appendix by Figure B.7.1) where the variables coding for these events will be predictors.

Based on the outcome of the Boruta algorithm, models might be used to investigate further the relationship between these variables and indwell time.

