6.6 Device Failure, Malfunctions and Defects

PIVC failure in the current study is defined as:

1. An inability to flush or collect blood through the PIVC
2. The removal of the PIVC based on medical doctor's assessment of an AE

A device rescue decision tree (see Appendix 16.5 of the study protocol) will be utilized to identify if the PIVC has failed.

7 Safety Analysis

Sufficient detail on summarizing safety data, e.g., information on severity, expectedness, and causality; details of how adverse events are coded or categorized; how adverse event data will be analyzed is provided in a separate document (i.e., a safety management plan).

8 Interim Analysis Plan

No interim analysis has been planned.

9 References

- [1] R Core Team. *R: A Language and Environment for Statistical Computing*. R Foundation for Statistical Computing, Vienna, Austria, 2016. URL <https://www.R-project.org/>.
- [2] Miron B. Kursa and Witold R. Rudnicki. Feature selection with the Boruta package. *Journal of Statistical Software*, 36(11):1–13, 2010. URL <http://www.jstatsoft.org/v36/i11/>.

10 SAP Revision History

Version Number	Rationale for Change	Section or Page Affected	Description of Change
1.0	Original SAP		

11 Appendix

A Tables

A.1 Demographics

Table A.1.1: Numerical Summary of Subjects Demographics, per Group (i.e. Gauge) and Overall

Characteristic	20G	22G	Overall
Age (years)			
Mean	42.35	39.87	41.11
95% Mean CI	37.42, 47.07	34.77, 44.98	37.51, 44.70
Median	45.15	39.45	42.15
SD	11.22	12.14	11.61
Min, Max	24.2, 56.3	23.9, 57.4	23.9, 57.4
Total Count	20	20	40
Gender			
F	11 (55.0%)	9 (45.0%)	20 (50.0%)
M	9 (45.0%)	11 (55.0%)	20 (50.0%)
Total	20	20	40
Ethnicity			
Non Hispanic / Latino	18 (90.0%)	19 (95.0%)	37 (92.5%)
Hispanic / Latino	2 (10.0%)	1 (5.0%)	3 (7.5%)
Total	20	20	40
Race			
Asian	6 (30.0%)	8 (40.0%)	14 (35.0%)
Other	7 (35.0%)	6 (30.0%)	13 (32.5%)
White / Caucasian	7 (35.0%)	6 (30.0%)	13 (32.5%)
Total	20	20	40
Height (cm)			
Mean	166.06	168.64	167.35
95% Mean CI	161.10, 171.26	163.55, 173.65	163.63, 171.10
Median	161.05	168.20	166.65
SD	12.09	11.78	11.85
Min, Max	151.2, 185.6	150.4, 188.6	150.4, 188.6
Total Count	20	20	40
Weight (kg)			
Mean	67.92	76.78	72.34
95% Mean CI	63.44, 72.27	73.23, 80.32	69.18, 75.43
Median	72.50	76.10	74.75
SD	10.41	8.34	10.34
Min, Max	52.8, 81.6	63.5, 88.7	52.8, 88.7
Total Count	20	20	40
BMI (kg/m²)			
Mean	22.40	22.90	22.65
95% Mean CI	21.25, 23.55	21.85, 24.00	21.88, 23.45
Median	23.00	23.50	23.00
SD	2.68	2.55	2.60

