S019	22G	2mL	155.16	No	No	44.12
S019	22G	6mL	165.42	No	No	116.40
S020	20G	2mL	204.74	Yes	Yes	41.08
S020	20G	6mL	216.52	Yes	Yes	94.47

D Additional Figures

D.1 PIVC Rescue Decision Tree

Figure D.1.1: PIVC Rescue Decision Tree for Flush Procedures

[figure not shown]

Figure D.1.2: PIVC Rescue Decision Tree for Aspiration Procedures

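### Flush duration and peak pressure are derived with no rule for failed or rescued flushes, so a trace from the failing session can be ranked as a predictor of the indwell-time failure it records (SAP 5.1.7 and 5.2.3.2)

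*SAP*

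**What the plan says.** The derivation is in SAP 5.1.7. Both flush variables are "derived from the pressure trace from a 3 to 10 mL saline flush performed upon first accessing the device at each time point". Time zero is the start of the pressure spike, and "The time point at which the spike in positive pressure returns to baseline will indicate completion of the flush". Equation 2 gives duration as the difference between the two, and Equation 4 takes peak pressure from the same interval. A second duration is offered: "Alternatively, the duration of the flush could be reduced to the time between the max pressure and the completion time point". Equation 3, printed directly beneath, instead subtracts time zero from the time of maximum pressure.

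The use is in SAP 5.2.3.2: "Manual flush variability will be evaluated using duration of flush and characteristics of Flush pressure profile obtained on in-line pressure measurements". The variables are summarised by time point and entered as predictors in a Boruta survival random forest. Further models relating them to indwell time may follow.

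Flush failure is recorded elsewhere. SAP 6.6 lists "An inability to flush or collect blood through the PIVC" as a form of device failure. SAP 5.2.1.1 identifies it for the survival analysis by "Flush: Variables DEFLSSU equal to “N” and DEFLSRS equal to “N” from table INFL". SAP 5.2.1.3 adds tabulations of "Failure remediation counts, which steps are described in the PIVC rescue decision trees for flush and aspiration procedures", pointing to Appendix D, where the flush tree is captioned "Figure D.1.1: PIVC Rescue Decision Tree for Flush Procedures". The tree itself is not shown in the text available for this review.

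**The concern.** Return to baseline marks completion only if the saline was delivered. If the operator meets resistance and stops, pressure also falls back to baseline, and Equation 2 yields a number all the same. Nothing in 5.1.7 or 5.2.3.2 tells the analyst to treat that number differently.

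Two things are at stake. The lesser is the descriptive summary. Manual flush variability is meant to describe technique, and mixing delivered flushes with failed or rescued ones would blur it, more so for the device that fails more often.

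The greater is the ranking. When a catheter fails at the flush, the trace from that session is recorded at the event. Used as a predictor, it lets the outcome leak into the covariate. Flush duration or peak pressure could then appear to drive indwell time when it only marks the failure.

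**Working it through.** No figure stated in the plan depends on this point, so the main check is a reading of the text. A calculation then bounds how many traces could be affected.

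**1. Is there a success condition?** No. SAP 5.1.7 sets completion by pressure alone, without reference to delivered volume, success or rescue.

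**2. Would a failing flush be on the transducer?** Yes, if it fails at first access. Protocol 7.3 has the catheter flushed while pressure is logged, before blood collection. SAP Table 2.7.1 places the pressure measurement at the start of each of the seven sessions.

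**3. Are the failure flags joined to the traces?** Not in any section.
- SAP section 3 has sponsor R&D extract profile and duration with a LabView routine and pass the results to the statistician as a csv file.
- SAP 5.2.1.1 uses the INFL flags only to define the survival event.
- SAP 5.2.1.2 and 5.2.1.3 use failure and remediation records only for counts. SAP 5.2.1.2 does discard failure records later than the first; the traces have no comparable rule.
- SAP 5.2.5 rules out imputation but does not say whether a failed-flush trace counts as missing.

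**4. Is the failing session kept out of the ranking?** Not by anything written. SAP 5.2.3.2 sets no time limit on the predictors. Protocol 10.7 had confined exploratory endpoints in the regression to those collected at baseline.

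**5. How many traces could be affected?** Inputs:
- Median times to failure of 1 and 3 days (SAP 2.4), taken as exponential, with 40 catheters of each length (40 participants, one of each).
- Accesses at about 0.25, 6, 24, 30, 48, 54 and 72 h (SAP Table 2.7.1).
- The share of failures that occur at the flush is not documented; 25% to 100% is assumed.

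Survival to time t with median m hours is S(t) = 0.5^(t/m). Expected flush attempts per catheter are 1 + S(0.25) + S(6) + S(24) + S(30) + S(48) + S(54).
- m = 24: 1 + 0.993 + 0.841 + 0.500 + 0.420 + 0.250 + 0.210 = 4.21 attempts. P(fail by 72 h) = 1 - 0.5^3 = 0.875.
- m = 72: 1 + 0.998 + 0.944 + 0.794 + 0.749 + 0.630 + 0.595 = 5.71 attempts. P(fail by 72 h) = 1 - 0.5 = 0.500.

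Total attempts: 40 × (4.214 + 5.709) = 396.9. Total failures of any mode: 40 × (0.875 + 0.500) = 55.

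| Flush share of failures | Failing-flush traces | All | 1-day median | 3-day median |
|---|---|---|---|---|
| 25% | 13.75 | 3.5% | 5.2% | 2.2% |
| 100% | 55 | 13.9% | 20.8% | 8.8% |

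The share differs between lengths because the planning failure rates differ. Flushes that were rescued and then succeeded would add to it; the documents give no rate for these.

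The SAP's mock tables give 46 flush failure modes (Table A.5.1) over 476 catheter-visits (Table A.10.1), or 9.7%. These are dummy counts, and the denominator is thrombus observations rather than flush traces, so the figure is not evidence of size.

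**The case against.** The strongest reply is that the SAP is silent, not wrong. A reader might infer that the plan applies its completion rule knowingly to failed flushes, so that an abandoned push enters the data as a completed one and distorts the endpoint. The documents do not support that. INFL records the failure, and the remediation tables record rescue steps. Per-device failure modes (Table A.5.2) and remediation counts (Table A.7.1 and its promised per-device version) are already planned. What is missing is only the link from those records to the duration and peak-pressure variables.

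Three further points stand:
- The decision tree is known only by its caption, and the extraction routine cannot be seen. Either may handle failed attempts sensibly.
- The most natural reading of first access is the first attempt, so a duration that spans the rescue is an unlikely outcome.
- Even the direction of bias in duration is open. An abandoned push may be short, while slow pushing against resistance may be long.

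Two points do not rescue the plan. The alternative duration is no way out: its words and Equation 3 disagree, and under either reading it comes from the same trace. And that 5.2.3.2 does not expressly name the failing-session trace as a predictor is little comfort, because nothing written excludes it.

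A fair warning about remedies also stands. Keeping only unrescued, delivered flushes selects on outcome and removes more traces from the device that fails more often. High-resistance flushes are arguably part of a pressure profile. That argues for showing them separately, not for leaving them mixed.

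**Conclusion.** The point holds as a gap in the exploratory flush analysis. Followed as written, 5.1.7 and 5.2.3.2 allow the trace from a failing session to act as a predictor of the failure that defines indwell time, although the flags needed to prevent this already exist.

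The 3.5% to 13.9% range rests on the planning medians, exponential failure and the assumed 25% to 100% flush share. It bounds how many traces could come from a failing flush; it does not measure bias, which cannot be computed from the documents. Distortion is a risk, not a demonstrated effect.

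Consequence is low. This is an exploratory endpoint in a feasibility study without acceptance criteria, and the log-rank and Cox analyses do not use flush duration or pressure. It is a worthwhile clarification rather than a necessary correction.

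**What to change.** In SAP 5.1.7:
- State that the trace of the first attempt at each session is used.
- Merge each trace with DEFLSSU and DEFLSRS from INFL.
- Summarise flushes delivered without rescue separately from failed or rescued ones, keeping the latter on display rather than discarding them.
- While the section is open, reconcile the wording of the alternative duration with Equation 3.

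In SAP 5.2.3.2, use only traces from sessions before the failure session as predictors of indwell time.

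The cost is a merge on existing variables and a few sentences; no new data are needed. The main flush summary will hold fewer traces, with more removed from the device that fails more often, which is why the failed and rescued traces should still be shown. The predictor rule also drops a delivered flush when a blood draw fails later in the same session, and leaves no flush predictor for a catheter that fails at its first session.
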